3.0 Objectives

3.1 Primary Objective

To evaluate the safety and efficacy of repeated daily oral administration of macimorelin at different doses for 1 week in view of a development for the treatment of cachexia based using the following parameters:

1. Change of body weight (kg) between day 1 and day 7
2. Change of IGF-1 plasma levels between day 1 (prior to dosing) and day 7
3. Change of quality of life score (Anderson Symptom Assessment Scale, FACIT-F) between day 1 and day 7

Hypothesis: One week administration of Macimorelin will be well tolerated and will improve body weight, plasma IGF-1, and quality of life compared to one week administration of placebo in patients with cancer cachexia.

3.2 Secondary Objectives

1. Food intake as measured by a food diary to be recorded for three days before days 1 and 7 and by a test meal done at screening and on day 7
2. Change of appetite measured by a validated visual analogue scale (VAS) between screening and day 7
3. Body composition as measured by bio-impedance analysis (BIA) and dual energy x-ray absorptiometry (DXA) on days 1 and 7
4. Muscle strength as measured by handgrip strength (HGS) and stair climbing power (SCP)
5. Resting energy expenditure (REE) as measured by indirect calorimetry
6. Change in systemic blood parameters (GH, IGF-1, CRP, IL-6, TNF- α , and glucose) between day 1 and day 7
7. Changes in reward from food as measured by brain functional Magnetic Resonance Imaging (fMRI)
8. Changes in functional brain connectivity as assessed by Resting State Functional Connectivity (RSFC) imaging and Diffusion Tensor Imaging (DTI)

Hypothesis: One week administration of Macimorelin will improve food intake, appetite, body composition, HGS, SCP, REE, systemic blood parameters, reward from food, and functional brain connectivity compared to one week administration of placebo in patients with cancer cachexia.

3.3 Safety Objectives

1. Clinical laboratory parameters: CBC, CMP, UA
2. Vital signs
3. ECG changes at day 1, day 7 and post-study visit
4. Recording of adverse events from day 1 to day 7

Hypothesis: One week administration of Macimorelin will be well tolerated with no serious adverse events in patients with cancer cachexia.

4.0 Resources and Personnel

Research procedures will be conducted within the VAPSHCS at [name] dedicated research spaces and at the Clinical Research Unit (CRU). [name] will oversee all study procedures including recruitment, consenting, administering surveys, data analysis, and coordination of all regulatory activities. Approved study staff (i.e. research nurses, postdoctoral fellows, study coordinators) will also carry out these procedures under the supervision of [name]. [name] and approved study staff will have access to protected health information. CRU staff may be contracted to perform study procedures in the case of an approved study staff member being unavailable. CRU staff will not have access to protected health information.

5.0 Study Procedures

5.1 Study Design

This is a double-blind, randomized, placebo-controlled trial to test the effects of the ghrelin mimetic macimorelin in cancer-cachexia patients after one week of administration. Adequate efficacy will be defined as a ≥ 0.8 kg of body weight gain or a ≥ 50 ng/mL increase in plasma IGF-1 levels or an improvement in quality of life questionnaires of at least 15% compared to placebo. The timeline of the study procedures are as follows:

	Screening: Day -24 to Day -1	Baseline: Day 1	Day 7: assessment/end of treatment	Post-study visit: 14 +/- 3 days after end-of-treatment
Informed Consent	X			
History and exam¹	X	X	X	X
AEZS-130 administration		X	X	
PD²		X	X	
ECG and Safety Labs³	X	X	X	X
Body Composition Analyses⁴		X	X	

Functional performance assessment⁵		X	X	
Resting energy expenditure⁶		X	X	
Questionnaires⁷		X	X	
Laboratory assays⁸		X	X	
Appetite and food intake assessment⁹	X		X	
MRI	X		X ¹⁰	
Adverse Events		X ¹⁰	X	X

Footnotes: Patients will receive treatment daily between days 1 and 7. Dosing on days 1 and 7 will take place in the clinic. Patients will take the drug at home on days 2-6. All tests will be done before dosing unless otherwise noted.

¹ Exam will include body weight measurement and a complete physical exam.

² Pharmacodynamics (PD) will be assessed before and 1 hour after dosing with measurements of GH.

³ Safety labs will include: CBC with Diff, comprehensive metabolic panel, and UA (including hCG for females). On days 1 and 7 ECG will be performed before and 1h after dosing.

⁴ Tests include bioimpedance analysis and dual energy x-ray absorptiometry.

⁵ Functional performance will be assessed by: a) handgrip strength, b) stair climbing power, c) activity level

⁶ Resting energy expenditure will be assessed by indirect calorimetry.

⁷ Questionnaires will include: The Eastern Cooperative Oncology Group (ECOG), and Karnofsky Scales, Anderson Symptom Assessment Scale (ASAS) and Functional Assessment of Chronic Illness Therapy-Fatigue (FACIT-F).

⁸ This will include measurements of glucose, IGF-1, GH, IGFBP-3, IL-6, CRP, and TNF-alpha.

⁹ Appetite will be assessed by a VAS before and 1h after breakfast; food intake will be assessed by a food diary. A test meal will be given at screening and 1h after dosing on day 7.

¹⁰ After dosing

Upon completion of the Day 1 procedures, allowing for procedure exemptions where applicable, the subject will be paid \$100 by check. Upon completion of the Day 7 procedures, allowing for procedure exemptions where applicable, the subject will be paid an additional \$100 by check.

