Specific aim: to determine the role of macimorelin on appetite, food intake, energy expenditure, inflammation, food reward, and QOL in CACS. In this double-blind, placebo-controlled trial, subjects with CACS will be randomized to placebo (N=2) v. macimorelin (N=6). Comparisons will be made between groups for changes from baseline in appetite (visual analogue scale), food intake (food diary and test meal), body weight, serum cytokines, REE (indirect calorimetry), food reward (fMRI), and QOL (questionnaires).

Significance: There is currently no effective therapy for CACS. This study will increase our understanding of the brain mechanisms mediating CACS, a necessary step in the development of effective therapies. These results are expected to open new avenues for treating symptoms associated with cancer and to improve QOL in this population. The present proposal will: a) Establish for the first time the extent to which abnormalities in food reward contribute to CACS in humans; b) Validate the use of fMRI in the study of cancer-related appetite regulation in humans which until now relies heavily in rodent data; and c) Establish the role of macimorelin in this setting and provide insight into its mechanisms of action by establishing the relative contribution of changes in food intake, food reward, and REE.

List of Abbreviations

AEZS	Æterna Zentaris
ALT	Alanine transaminase (SGPT)
ASAS	Anderson Symptom Assessment Scale
AST	Aspartate transaminase (SGOT)
BIA	Bioimpedance Analysis
BMI	Body mass index
BUN	Blood urea nitrogen
CBC	Complete blood count
CFR	Code of Federal Regulations
CMP	Comprehensive Metabolic Panel
CO2	Carbon dioxide
CRP	C-Reactive Protein
CPRS	Computerized Patient Record System
CTCAE	Common Terminology Criteria for Adverse Events
DLDC	Dan L. Duncan Cancer Center
DXA	Dual Energy X-Ray Absorptiometry
DMC	Data Monitoring Committee
DTI	Diffusion Tensor Imaging
ECOG PS	Eastern Cooperative Oncology Group Performance Status
ECG	Electrocardiogram
FACIT-F	Functional Assessment of Chronic Illness Therapy-Fatigue
FDA	Food and Drug Administration
FSH	Follicle-Stimulating Hormone

fMRI	Functional Magnetic Resonance Imaging
GCP	Good Clinical Practices
GH	Growth Hormone
GHS-R	Growth Hormone Secretagogue Receptor
HbA _{1c}	Hemoglobin A _{1c}
hCG	Human Chorionic Gonadotropin
HGS	Handgrip strength
HIPAA	Health Information Portability and Accountability Act
HIV	Human immunodeficiency virus
hs-CRP	High sensitivity CRP
H&P	History and Physical

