2.0 Introduction

2.1 Synopsis

This study is a continuation of a sequential protocol initiated at the Houston VA wherein safety and assessment of a daily, weeklong administration of an initial Macimorelin dose was assessed before proceeding with additional assessment of various doses. The following flow chart summarizes that study design:

Safety and efficacy of the Group 1 dose was completed while still an active protocol in Houston. It was determined that there were no safety issues but there was inadequate efficacy (defined as a ≥ 0.8 kg of body weight gain or a ≥ 50 ng/mL increase in plasma IGF-1 levels or an improvement in quality of life questionnaires of at least 15% compared to placebo). The protocol continued with Group 2 recruitment only. One patient completed the Group protocol before the study was moved with [name] to the Puget Sound VA. Herein we submit the detailed protocol for continuation with Group 2 only. **Note: placebo patients from Groups 1 (N=4) and 2 (N=2) will be combined for comparison to the Macimorelin group(s).** A synopsis of the protocol is provided below.

Title	Pilot clinical trial of Macimorelin to assess safety and efficacy in patients with cancer cachexia
Principal Investigator/ Investigational Site/Sponsor	[name], PhD VA Puget Sound Health Care System [name]

	
[name] [name] [contact] [contact] [contact]

Drug source/Medical Monitor	
Drug source: Æterna Zentaris, Inc [name]
 
Medical Monitor: [name], PhD VA Puget Sound Health Care System [name] [name] [name] [contact] [contact] [contact]

Study Duration	November 2016-November 2017 (estimated)

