Study Objectives	
Primary Objectives: To evaluate the safety and efficacy of oral administration of macimorelin daily for 1 week in view of a development for the treatment of cachexia based using the following parameters:
 
 1. Change of body weight (kg) between day 1 and day 7 2. Change of plasma IGF-1 between day 1 (prior to dose) and day 7 3. Change of quality of life score (ASAS, FACIT-F) between day 1 and day 7 
Secondary Objectives:
 
 1. Food intake as measured by a food diary to be recorded for 3 days before days 1 and 7 and by a test meal done at screening and on day 7. 2. Change of appetite measured by a validated visual analogue scale (VAS) between day 1 and day 7. 3. Body composition as measured by bio-impedance (BIA) and dual energy x-ray absorptiometry (DXA) on days 1 and 7. 4. Muscle strength as measured by handgrip strength (HGS) and stair climbing power (SCP). 5. Resting energy expenditure (REE) as measured by indirect calorimetry. 6. Change in IGFBP-3, GH, CRP, IL-6, TNF-α, and glucose between

	
day 1 and day 7.
 
7. Changes in reward from food as measured by brain functional Magnetic Resonance Imaging (fMRI).
 
8. Changes in functional brain connectivity as assessed by Resting State Functional Connectivity (RSFC) imaging and Diffusion Tensor Imaging (DTI).
 
Safety Objectives:
 
 1. Clinical laboratory parameters: complete blood count (CBC), comprehensive metabolic panel (CMP), urinalysis (UA) 2. Vital signs, 3. Electrocardiogram (ECG) at days 1 and 7 before and 1 hour after dosing and on the post-study visit. 4. Recording of adverse events from day 1 to day 7 
Long-Term Objective:
 
The long-term objective of this research is to determine the extent to which the ghrelin mimetic macimorelin will affect energy intake and energy expenditure, and the effect that these changes will have on body weight, body composition, and functional performance in cancer patients with cachexia

Population	Approximately 8 patients with diagnosis of cancer induced cachexia (defined as a weight loss of $\geq 5\%$ body weight in the 6 months prior to screening) will be randomized 3:1 to macimorelin vs. placebo.

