2.5 Safety of Ghrelin in the Setting of Cancer

As with all clinical trials, the issue of safety is our first priority. The GHS-R is expressed in many normal and tumor tissues including breast, thyroid and prostate and in-vitro studies have given conflicting results (19)(20). Administration of a growth factor such as ghrelin or GH to tumor-bearing individuals raises potential concerns of stimulation of tumor growth, particularly through elevation of IGF-1. However, when whole animal tumor growth studies have been conducted to evaluate the effect of increasing GH tone, the results have generally indicated a beneficial effect (21-23). There have been publications implicating IGF-1 in oncogenic potential; in addition, there have been reports indicating the therapeutic potential of the major binding protein, IGFBP-3, in attenuating oncogenic behavior either via its ability to bind IGF-1 or via direct, IGF-independent actions. Consequently, it may be that the balanced effect of a growth hormone based intervention

to increase both IGF-1 and IGFBP-3 may be responsible, in part, for some of the apparent discrepancies. Hanada et al.(24) tested the effects of ghrelin in a different model of tumor-induced cachexia. In this experiment, cachexia was reversed by the administration of ghrelin and tumor size remained unchanged, decreasing the tumor/carcass ratio. The composite preclinical literature indicates beneficial effects of ghrelin-based intervention in cancer-related weight loss models; it increases lean body mass and in some studies reduces disease progression relative to the untreated state.

More importantly, administration of ghrelin mimetics was well-tolerated and safe in preliminary studies where approximately 40 patients with cancer-induced cachexia were exposed for at least 3 months (25). Consequently, the overall conclusion from these preclinical and clinical in-vivo evaluations is the likelihood that activation of GHS-R will support and improve host function without producing detrimental effects on the underlying malignancy.

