2.6 Rationale for Macimorelin Administration in Cancer Cachexia

Macimorelin is an orally active ghrelin mimetic and growth hormone secretagogue. Ghrelin is the endogenous ligand for the growth hormone secretagogue receptor (AKA ghrelin receptor, GHS-R) (26, 27). Pharmacological treatment of rats and mice with ghrelin stimulates food intake and increases body weight (28). Also, ghrelin reduces fat oxidation and increases adiposity (29). Smith et al. have shown that *Ghsr* ^{-/-} mice are refractory to the stimulatory effects of ghrelin on GH release and appetite, confirming that the GHSR-1a is a physiologically relevant ghrelin receptor (30).

Activation of GHSR-1a by ghrelin mimetics (growth hormone secretagogues, GHS) also induces GH secretion (31) and it increases food intake and body weight (32, 33). In non-cancer patients, ghrelin mimetics increase body weight and reverse the negative nitrogen balance induced by starvation independently of their orexigenic effects. These findings suggest that ghrelin's effects are not entirely mediated through an increase in appetite and that other mechanisms, such as a decrease in energy expenditure, are involved (34). Ghrelin administration decreases energy expenditure in non-cancer human and animal models (35, 36). In two small groups of cancer patients, a single infusion of ghrelin was well tolerated, increasing appetite and food intake in one of the studies (9) but not in the other (37).

Because ghrelin is a peptide with a half-life of 30 minutes, its efficacy in humans is limited unless it is administered parenterally as a continuous infusion. Ghrelin mimetics such as macimorelin are non-peptidic, orally available, small molecules that have a relatively long half-life allowing for once-a-day administration. These compounds have been in clinical trials for over a decade and our group and others have demonstrated their safety and efficacy (33, 38).

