5.12 Study Evaluations

5.12.1 Quality of Life Measures

The study will include the following patient-reported Quality of Life Instruments: ASAS and FACIT-F. These instruments have been previously used and validated in clinical research investigations. These instruments must be completed by the patient before other procedures are done at follow-up visits. When the patient has completed the questionnaires, the forms will be collected from the patient and entered into the case report forms (CRFs) by authorized site personnel. Site personnel should review the forms to ensure all questions were answered and that the intended answers were clearly marked before the patient leaves the study site. The site personnel should ask the patient to complete any missed questions and to clarify any unclear answers. If a patient is unable to complete any or all of the questions, the reason must be documented in the source documentation and in the CRF.

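### Is the adequate-efficacy rule unsound because IGF-1 alone can satisfy it, when section 3.1 expects weight, IGF-1 and quality of life all to improve?

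*Combined protocol and SAP*

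**What the plan says.** Section 5.1 defines adequate efficacy through three limbs joined by *or*: a weight gain of at least 0.8 kg, an IGF-1 rise of at least 50 ng/mL, or a 15% quality-of-life gain. The last two limbs read "increase in plasma IGF-1 levels or an improvement in quality of life questionnaires of at least 15% compared to placebo". The 2.1 Synopsis gives the same definition and records its use on the Group 1 dose: "It was determined that there were no safety issues but there was inadequate efficacy".

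The hypothesis in 3.1 is a joint statement, that one week of macimorelin "will improve body weight, plasma IGF-1, and quality of life compared to one week administration of placebo". Weight, IGF-1 and quality of life are the three primary efficacy parameters in the Synopsis, 3.1 and 5.12.13.2, with no ranking. On quality of life, 5.12.1 says "The study will include the following patient-reported Quality of Life Instruments: ASAS and FACIT-F", without saying how the two scales combine.

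Section 5.12.13.1 describes a pilot and exploratory study. It summarises all efficacy variables by treatment, promises full disclosure of all endpoints, and intends the data for powering a larger trial. It does not mention the adequate-efficacy rule.

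**The concern.** An *or* rule set beside an *and* hypothesis can declare success when two of the three expected effects are absent or reversed. IGF-1 looks like the weakest limb to stand alone. Section 2.6 says "Macimorelin is an orally active ghrelin mimetic and growth hormone secretagogue", so a rise may show only that the drug acted on its axis. Section 2.5 notes that giving a growth factor to patients with tumours "raises potential concerns of stimulation of tumor growth, particularly through elevation of IGF-1", although it goes on to consider harm unlikely. The abstract's comparisons, which include "body weight, serum cytokines, REE (indirect calorimetry), food reward (fMRI), and QOL (questionnaires", leave IGF-1 out. So does the long-term objective, which concerns "the effect that these changes will have on body weight, body composition, and functional performance in cancer patients with cachexia".

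At stake is the conclusion drawn from the pilot. If the true IGF-1 difference were exactly 50 ng/mL with no weight effect, the IGF-1 limb would pass while observed weight favoured placebo in ½ × ½ = 25% of trials (20% if the two differences correlate at 0.3: 1/4 − asin(0.3)/(2π) = 0.20). Such a result would still be called adequate for cachexia.

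The sentence is also loose in three smaller ways. The placebo comparison is attached only to the last limb, the two scales are not combined, and the base of the 15% is not given.

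**Working it through.** The plan gives no SDs, alpha or power, so there is no stated figure to reproduce. The check asks what the IGF-1 limb adds, and what the obvious remedy (keeping only weight or quality of life as sufficient) would change.

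**Inputs**
- Macimorelin 6 (8 patients at 3:1); pooled placebo 4 + 2 = 6 (2.1 Synopsis).
- Each limb is read as a difference in mean change, with SE = SD × √(1/6 + 1/6) = 0.577 × SD.
- Assumed SDs are 1.0 kg, 30 ng/mL and 20 percentage points, giving SEs of 0.577, 17.32 and 11.55. The high set is 1.5, 50 and 30.
- ASAS and FACIT-F are assumed to correlate at 0.5, with both needed. Other correlations are 0 for the hand calculation.

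**Chance of each limb passing with an inert drug**
- Weight: 0.8/0.577 = 1.386, tail 0.0829.
- IGF-1: 50/17.32 = 2.887, tail 0.0019.
- Each scale: 15/11.55 = 1.299, tail 0.097. Both scales: 0.031.

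**Inert drug, whole rule**
- Three limbs: 1 − 0.9171 × 0.9981 × 0.969 = 0.113.
- Without IGF-1: 1 − 0.9171 × 0.969 = 0.111.
- High SDs (limb tails 0.1778, 0.0416, 0.0829): 1 − 0.8222 × 0.9584 × 0.9171 = 0.277, against 1 − 0.8222 × 0.9171 = 0.246.
- Base SDs with either scale enough (2 × 0.097 − 0.031 = 0.163): 1 − 0.9171 × 0.9981 × 0.837 = 0.234, against 1 − 0.9171 × 0.837 = 0.232.

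**Drug acting on IGF-1 only**
- True difference 50 ng/mL: 1 − 0.5 × 0.9171 × 0.969 = 0.556, against 0.111 without the limb.
- True difference 75 ng/mL: 25/17.32 = 1.443, so the limb passes 0.9255 of the time; 1 − 0.0745 × 0.8887 = 0.934, against 0.111.

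**Drug acting on weight only, true difference 0.8 kg**
- Without the IGF-1 limb: 1 − 0.5 × 0.969 = 0.516. With it the result is also 0.516.

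**All true effects exactly at threshold** (both scales pass with probability 1/4 + asin(0.5)/(2π) = 1/3)
- Any of three: 1 − ½ × ½ × ⅔ = 0.833.
- Weight or quality of life: 1 − ½ × ⅔ = 0.667.
- All three: ½ × ½ × ⅓ = 0.083.

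With a correlation of 0.3 between domains, simulation at the base SDs gives 10.7% against 10.6% (inert), 53.0% against 10.6% (IGF-1 only at 50), and 75.5%, 61.8% and 15% for the last three lines.

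**Reading the texts together.** Section 3.2 words its hypothesis in the same way for nine outcomes, and nobody would require all nine. Section 3.1 states expectations; 5.1 sets a screening threshold that comes from a sequential dose study. They answer different questions.

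**The case for a change.** The strongest opposing case is that 5.1 does not confine the rule to dose screening. It restates it for Group 2, where no further dose step is described, so the rule now serves only to label the result. If IGF-1 is simply a marker of drug action, calling an IGF-1-only drug adequate 56% of the time at 50 ng/mL, and 93% at 75 ng/mL, is misleading. A pilot excuses imprecision, not a definition at odds with its hypothesis.

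Part of this stands. The label can be earned through IGF-1 alone, and earning it does not show that 3.1 is supported. The rest does not carry the case for a change:

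- Section 2.2 says abnormalities in the GH/IGF-1 axis have been postulated to be pathogenic in cachexia, so the protocol does not treat IGF-1 as a bare marker. Footnote 2 to the 5.1 schedule assesses pharmacodynamics with GH.
- The argument from omission reaches the other limbs too. The abstract's hypothesis leaves out body weight, and the long-term objective leaves out quality of life.
- The limb is not met automatically by a GH secretagogue. Group 1 was found inadequate under this same rule, which means its IGF-1 limb was not met.
- Removing IGF-1 leaves another *or*. The threshold-case gap becomes 67% against 8%, instead of 83% against 8%.
- Group 2 would be held to a different definition from Group 1, after one Group 2 patient has already completed.

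The scale question is a real gap. At a true effect equal to the threshold, requiring both scales and accepting either give opposite answers in 1 − 2 × 1/3 = 33% of trials (25–40% for scale correlations of 0.7 to 0.3). The text does not settle the choice: the rule uses a plural for the questionnaires, while the endpoint lists refer to a score.

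**Conclusion.** No change follows. Letting IGF-1 count as one sufficient sign of activity in a one-week pilot of eight patients is a fair trade-off. It costs about 0.2 percentage points of false passes at the base SDs and about 3 at the high SDs. The large contrast, 56% against 11%, appears only when a real IGF-1 effect is assumed to have no value. Dropping the limb would leave the either-or structure in place and take a declared primary parameter out of the rule.

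The wording gaps are ones analysts would fill sensibly. The Design row of the Synopsis and 3.1 both make the comparison one of changes against placebo, and each scale's change can be shown on its own. Because 5.12.13.1 requires every endpoint to be summarised and disclosed, an IGF-1-only result would be visible as such. A larger trial would be powered from the reported means and SDs, not from the label. No Group 2 dose or stopping step depends on it.

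The probabilities rest on assumed SDs and correlations and are illustrative. The logical points do not depend on them.
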